### 4.2.2. Comparator

Treatment as usual is street outreach *without* a health specialism. There can be significant heterogeneity across street outreach services. Details of outreach delivery in comparator sites will be assessed through the process evaluation.

## 4.3. Intervention Dates

The intervention will be delivered for a duration of 17 months, commencing January 2025 until May 2026 (note the trial data collection ends earlier than the intervention delivery).

## Table 6: TIDier Framework\*

(Hoffmann, et al. 2014)

\*Note that the Tidier TIDieR Framework and intervention description will be updated as an output of the optimisation phase.

Brief Name: Provide the name or a phrase that describes the intervention
	
Outreach services with a nurse health specialism for people rough sleeping.

Why: Describe any rationale, theory, or goal of the elements essential to the intervention
	
The overarching rationale of the intervention is that nurses meet service users where they are rough sleeping, which increases contact with service users. Nurses have a respected identity as a health professional that service users may trust to support them. This trust can be enhanced by nurses having professional knowledge to identify and deliver the correct service provision and having the expertise and professional standing to secure service access. Nurses' identification of a health care need for service users can also ensure access to appropriate housing, as health care needs can result in an accommodation entitlement.

What (Materials): Describe any physical or informational materials used in the intervention, including those provided to participants or used in intervention delivery or in training of intervention providers. Provide information on where the materials can be accessed (such as online appendix, URL)
	
Standard and bespoke training is a key component of the intervention.
 
Standard Training: Standard nurse training modules (treating substance use etc.) will be made available to outreach nurses through CGL. This training is sourced from the Queens's Nursing Institute, LNNM, Fairhealth and Aneemo training and resource platforms.
 
Bespoke Training: Outreach nurses will receive a bespoke training package with a focus on supporting people rough sleeping. Four half day training sessions will be delivered by an expert

	
professional. Two will be delivered online and two will be delivered in person. These will be complemented by a range of other electronic resources. Training will include didactic learning and scenario-based interaction.


What (Procedures): Describe each of the procedures, activities, and/or processes used in the intervention, including any enabling or support activities
	
There are four key intervention components:
 
 
1) Outreach nurse training: Includes standard and bespoke training.
 
2) Outreach with specialism shifts: Outreach nurses accompany outreach teams to deliver healthcare on the street and arrange access to healthcare and housing.
 
3) Outreach nurse supervision and quality assurance: Clinical supervision of nurses by a Lead Nurse.
 
4) Service follow-up and Multi-disciplinary Team (MDT) meetings: Arrangement of follow-up healthcare and housing services after outreach sessions. Attendance at MDT meetings to advocate for the service user.
 

Who provided: For each category of intervention provider (such as psychologist, nursing assistant), describe their expertise, background, and any specific training given
	
 
1) Outreach nurse training  Standard training: Training will be facilitated by CGL and primarily provided through the Queens’s Nursing Institute, LNNM, Fairhealth and Aneemo.  Bespoke training: Training will be developed by [name] (expert advisor on health outreach intervention) and hosted by CGL.
 
2) Lead Nurse  The Lead Nurse based in CGL (equivalent to top NHS band 7) will oversee and line manage the 8 trained outreach nurses (equivalent to top NHS band 6).
 

### **3) Outreach nurses**

Outreach with a health specialism will be provided by eight appointed outreach nurses. Desirable competencies for the outreach nurses include:

- An advanced assessment course and/or significant experience of clinical triage in an A&E department
- History of working with people who have experienced homelessness
- A proven ability to assess and manage clinical risk independently
- Level 3 safeguarding training (including an understanding of self-neglect)
- Ability to directly prescribe (i.e. the ability to provide an immediate prescription) or to provide drugs by Patient Group Direction. Training could be provided to outreach nurses on Patient Group Direction if someone has an advanced assessment course but no prior Patient Group Direction experience (Dorney-Smith, 2021).

Based on previous case examples of outreach nurses, it has been suggested that they should be a band 7 equivalent to ensure they have the requisite experience and expertise (Dorney-Smith, N.D.).

### **4) Outreach teams**

Typically, 1-2 members of the designated outreach team will accompany the nurses during the outreach shifts. The number of accompanying outreach workers can be negotiated, but the key is that outreach nurses should not go alone.

	
5) Other professionals (for MDT meetings)
 
A range of partnering teams and professionals will be required to ensure that service users' complex needs can be met, and appropriate care can be planned. These can include (Dorney-Smith, 2022):
 
 
● Local Authority rough sleeping pathway lead
 
● Outreach team (beyond team immediately supporting intervention)
 
● Mental health teams
 
● Social worker
 
● Police
 
● Primary care physician
 

How: Describe the modes of delivery (such as face to face or by some other mechanism, such as internet or telephone) of the intervention and whether it was provided individually or in a group
	
 
1) Outreach nurse training: Will be delivered in person and online.
 
2) Outreach with health specialism shifts: Will be delivered in person on the street as direct service user contact.
 
3) Outreach nurse supervision and quality assurance: Will be delivered in a group or individual format online or via telephone. May entail occasional in-person meetings.
 
4) Service follow-up and MDT meetings: May be delivered online, via telephone or in person depending on the services that outreach nurses follow-up with or the meetings they attend.
 

Where: Describe the type(s) of location(s) where the intervention occurred, including any necessary infrastructure or relevant features
	
 
1) Outreach nurse training: Online activities will be remotely accessed through the relevant platform. The venue for in-person training is to be agreed.
 
2) Outreach with specialism shifts: Will be delivered mainly on the
 

	
street. Outreach teams will identify the location of the service users as they will have more experience and knowledge of their location.
 
3) Outreach nurse supervision and quality assurance: Online meetings will be remotely accessed through the relevant platform. The venue of in-person meetings will likely be at CGL offices.
 
4) Service follow-up and MDT meetings: Online meetings will be remotely accessed through the relevant platform. In-person meetings will be accessed at the location of the services that outreach nurses follow-up with.

When and how much: Describe the number of times the intervention was delivered and over what period of time including the number of sessions, their schedule, and their duration, intensity, or dose
	
Outreach nurse training:
 
A. Standard training: Training will be made available to outreach nurses on an ongoing basis. CGL will arrange a hosting platform and [name] will share resources to be hosted alongside training modules provided by the Queens’s Nursing Institute, LNNM, Fairhealth and Aneemo training and resource platforms.
 
B. Bespoke training: Training will be delivered as four half day sessions. Two will be delivered online and two will be delivered in person.
 
Their working week will be split as follows:
 
1) Outreach with health specialism shifts
 
It is recommended that outreach nurses will spend 60% of their week on shifts.

	
This should include a minimum of two shifts on the streets with service users, which should each take approximately eight hours (Dorney-Smith, N.D.).
 
2) Outreach nurse supervision, quality assurance, and training
 
The Lead Nurse will meet with the outreach nurses collectively on a weekly basis. This meeting will be conducted online. Each nurse will also have monthly (where possible) clinical supervision meetings with the Lead Nurse. This will take roughly 20% of their time.
 
3) Service follow-up and MDT meetings
 
Nurses will spend approximately 20% of their time ensuring data and information are complete and to secure follow-up services. This includes completing data used for the trial. They may also be required to spend time attending MDT meetings.


Tailoring: If the intervention was planned to be personalised, titrated or adapted, then describe what, why, when, and how
	
The intervention should always comprise delivery of the four central components. The outreach activities delivered to service users and the resulting follow-up activities will be personalised to the individual. Activities will also be dependent on services and resources available to outreach nurses. Based on previous outreach with a health specialism interventions, it has been recognised that the delivery model is flexible and fit for purpose and can be adapted well to ongoing changes (Dorney-Smith & Sivasathiaseelan, 2020).

Modifications: If the intervention was modified during the course of the study, describe the changes (what, why, when, and how)
	
To be completed at reporting stage.

How well (Planned): If intervention adherence or fidelity was assessed, describe how and by whom, and if any strategies were used to maintain or improve fidelity, describe them
	
Key fidelity measures will include:
 
 
Outreach nurse training 
 
● Completion of standard and bespoke training.
 
 
 
Nurse outreach with health specialism shifts 
 
● Delivering in outreach settings for approximately 15-16 hours per week
 
● Uptake of treatment/support offer
 
● Providing immediate treatment where relevant
 
● Manageable caseloads
 
 
 
Outreach nurse supervision and quality assurance 
 
● Number of supervision sessions between Lead Nurse and nurses
 
 
 
Follow-up services and MDT meetings 
 
● Follow-up services secured for service users where appropriate
 
● Uptake of follow-up service offer
 
● Number of MDT meetings attended by outreach nurses
 
 
 

How well (actual): If intervention adherence or fidelity was assessed, describe the extent to which the intervention was delivered as planned
	
To be completed at reporting stage.

## 5. PILOT CLUSTER RANDOMISED CONTROLLED TRIAL

### 5.1. Aim, Objectives and Research Questions

#### 5.1.1. Aim and objectives

The aim is to conduct a pilot cRCT to determine suggestive evidence of the intervention impacts and the viability of the trial methods. A set of evaluation feasibility criteria will be used to assess this (outlined in Table 8).

## 5.1.2. Research questions

The research questions are:

### 1 **Intervention viability**

- 1.1 Is the intervention acceptable to service users, Local Authorities, and nurses?
- 1.2 Are the intervention delivery staff able to engage service users?
- 1.3 Is the intervention delivered with fidelity?

### 2 **Defining treatment as usual**

- 2.1 Is it possible to accurately describe treatment as usual in control sites?

### 3 **Trial methods: randomisation and recruitment of Local Authorities (LAs)**

- 3.1 Is randomisation acceptable to LAs and why/why not?
- 3.2 What proportion of recruited LAs are retained throughout the trial?
- 3.3 Are there any potential ethical, practical, statutory, or other legal barriers that impact recruitment and randomisation processes?

### 4 **Trial methods: data collection procedures**

- 4.1 Are methods of data collection feasible and what refinements (if any) are needed?
- 4.2 To what extent can service users be followed up for data collection purposes?
- 4.3 What proportion of data is collected and completed for service users at baseline and follow-up?
- 4.4 Are outcome measures suitable and what refinements (if any) are needed?

### 5 **Impacts**

- 5.1 What are the potential impacts of the intervention on the housing situation of service users?
- 5.2 What are the potential impacts of the intervention on the health of service users?

Many of these research questions will be addressed through the Implementation and Process Evaluation. This section of the protocol focuses primarily on the impact component of the trial.

## 5.2. Study Design

### 5.2.1. Two-arm pilot cluster randomised controlled trial

The study design is a two-arm pilot cluster randomised controlled trial (cRCT). Local Authorities (LAs) are the unit of randomisation. 16 eligible LAs will be randomly assigned by an independent statistician in a 1:1 ratio (8 LAs per arm) to receive funding to embed a health professional as part of the outreach team (a qualified nurse) or remain with their usual practice.

### 5.2.2. Randomisation technique

Block randomisation of varying sizes will be used, stratified by the Rough Sleeping Initiative (RSI) funding allocation 2022-2025, per individual rough sleeping (£) of the 16 eligible LAs. Strata are created based on the median RSI funding allocation of the 16 LAs. The rationale for selecting the LA RSI funding allocation per individual rough sleeping population as a balancing variable is because it is likely to be correlated with availability of rough sleeping services it is ringfenced for. The availability of services is likely to influence outcomes of housing situation in a future RCT. A random allocation sequence will be generated in blocks using the *ralloc* program in Stata 17. More details on this are available in the randomisation protocol in Appendix A.

## 5.3. Research Setting

The pilot RCT will be conducted in England. All LAs that return an expression of interest to CHI will be eligible for the sampling frame. Essential criteria for inclusion of the LAs are outlined in Table 7. CHI will select 16 Local Authority areas in England for the study, based on assessment and scoring via a rubric (see Appendix B). Each LA will individually meet with CHI in an introductory meeting, meet CGL, and sign a contract. More details on this are available in the randomisation protocol in Appendix A.

## 5.4. Masking

This is an unblinded study where LA staff, research teams, and data collectors will know the intervention allocation. The randomisation schedule will be stratified and will be prepared and held by an independent statistician within the CTR. Allocations of LAs will be blinded from the trial statisticians conducting the final analysis. All data collectors and participants will not be blinded at baseline or follow-up data collection.

## 6. POPULATION

### 6.1. Eligibility

The following criteria will be used to determine eligibility for study inclusion:

**Table 7: Pilot cRCT Inclusion and Exclusion Criteria**

	Inclusion criteria	Exclusion criteria
Local Authority recruitment	
 
Have sufficient numbers of people rough sleeping to potentially receive health outreach support (expect around 40 people rough sleeping to come through the service during the baseline period).
 
	
 
Local Authority areas which already have an embedded health specialist who does shifts with the local outreach team.
 

	
 
• Have an outreach team.
 
• Be in reasonable distance (defined by CHI) to a CGL clinical service (to act as a clinical base to host the nurse).
 
• Willingness to be involved and support data collection procedure.
 
	
People living on the streets and included within Local Authority and CGL routine data collections	
 
• People living on the streets (defined as seen sleeping on the streets on at least 6 separate occasions over a period of up to 6 months) and included within CGL or Local Authority routine rough sleeping data collections.
 
	
 
• People rough sleeping who are not living on the streets and not included in LA or CGL routine data collections.
 

The study inclusion criteria focus on people living on the streets for two main reasons. First, it is likely that people living on the streets will be better known to outreach services, therefore significantly increasing the likelihood of successful baseline and follow up data collection. Second, this subgroup of people rough sleeping are further away from being accommodated than peers who spend less time sleeping on the streets, and therefore the intervention has potential for greatest impact.

Crucially, nurses will be permitted to support other people rough sleeping, but trial eligibility criteria will focus only on those living on the streets. The IPE and economic evaluation will capture data from nurses on the time spent with the eligible vs ineligible trial population.

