## **8. DATA COLLECTION**

### **8.1. Data Collection Methods**

In intervention sites, housing situation data (primary outcome), health status data (secondary outcome), and health service interaction data (secondary outcome) will primarily be collected by nurses as part of their normal routine service delivery at baseline, 3 and 6 months. They will also be supported by a dedicated CGL team member and outreach workers. At follow-up, service users will either be recontacted on the streets, contacted using known telephone numbers, or nurses/CGL team member will seek to locate individuals through other service providers (e.g. hostels and day centres). CGL will amend their routine data collection platform to capture outcome data.

In control sites, housing situation data (primary outcome), health status data (secondary outcome), and health service interaction data (secondary outcome) will be collected by outreach workers as part of their normal routine service delivery at baseline. At follow-up, a dedicated CGL team member will support the collection of follow-up data at 3 and 6 months in control sites. Service users will either be recontacted on the streets, using known telephone numbers, or the CGL team member will seek to locate individuals through other service providers (e.g. hostels and day centres). The CGL team member will work across all control sites, potentially travelling between them to aid sites in collating data. They will also assist the local teams in their data uploading and in tracking service users who have previously been included as part of the study and following-up with these service users.

Data will be manually input into the CGL managed CRi Information System (CRiIS). For intervention sites, baseline data will be entered by the outreach nurse, and follow-up data with assistance from a CGL team member. For control sites, the relevant data extracts will be provided to CGL, then all data will be manually entered into CRiIS by the CGL team member.

As data will be collected by nurses and/or outreach workers ('users') as part of their everyday service delivery, there will be an element of user preference determining how it is collected. Staff can either enter data directly into the database using a CGL provided mobile device whilst they are with the service user or make paper notes and transfer them at the office via the online portal.

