**Table 9: Data Collection Procedures and Assessment Timeline**

Assessment point	Type of data	Data collection approach
First contact (four-week window to collect baseline)	Contact recording and eligibility assessment.	Nurses and outreach workers. On the street/in the community.
Baseline	Baseline characteristics (age, sex, gender, nationality, care experienced, left an institution in the last 85 days – see Appendix F), primary and secondary outcomes (pre-intervention).	Nurses and outreach workers. On the street/in the community.
Interim contact data*	Contact date for each contact occurrence with service user to record data and/or to receive treatment, care or advice.	Nurses and outreach workers and CGL team member. On the street/in the community (intervention sites only).
Midline (3 months after baseline – 4-week window to complete)	Primary and secondary outcomes including reason for non-contact if applicable.	Nurses, outreach workers, and CGL team member. On the street/in the community, telephone (if contact details provided), through other organisations (e.g. NHS).
Interim contact data*	Contact date for each contact occurrence with service user to record data and/or to receive treatment, care or advice.	Nurses and outreach workers and CGL team member. On the street/in the community (intervention sites only).
Endline (6 months after baseline – 4-week window to complete)	Primary and secondary outcomes including reason for non-contact if applicable	Nurses, outreach workers, and CGL team member. On the street/in the community, telephone (if contact details provided), through other organisations (e.g. NHS).

\*Interim contact data collected in intervention sites only to assess level of contact per service user, treatment, care or advice given (anonymised), and to facilitate follow-up data tracking

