### 10.1. Analytic Sample

All analyses will be on an intention to treat (ITT) approach and will include service users that are included in the study, irrespective of how much intervention is received.

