#### **9. Fallback procedures in case of primary system failure**

All LAs will be randomised at the same time and ahead of recruitment and baseline collection. No fallback procedure is required.

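### Who enters the housing analysis could depend on the arm, because people are identified after allocation, during delivery, and in intervention sites partly by the nurse

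*Protocol*

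**What the plan says.** **Order of events.** Appendix A, section 9: "All LAs will be randomised at the same time and ahead of recruitment and baseline collection". Appendix A, section 10 then has each LA told its arm. Delivery starts in January 2025 (Section 4.3). Baselines run from January to October 2025 (Table 4, Section 12.2.3), wholly inside the delivery period. Section 5.4 leaves all data collectors unmasked.

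**Who qualifies.** Table 7 requires a person to have been "seen sleeping on the streets on at least 6 separate occasions over a period of up to 6 months" and to appear in CGL or LA routine data. Directly below it: "Crucially, nurses will be permitted to support other people rough sleeping, but trial eligibility criteria will focus only on those living on the streets".

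**Who identifies and records.** Table 9 assigns the first-contact step, "Contact recording and eligibility assessment", to nurses and outreach workers, and allows four weeks from first contact to take the baseline. Under Section 8.1, outcome data in intervention sites "will primarily be collected by nurses as part of their normal routine service delivery at baseline, 3 and 6 months", with support from outreach workers and a CGL team member. In control sites they "will be collected by outreach workers as part of their normal routine service delivery at baseline".

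**Who is analysed.** Section 10.1 calls the approach intention to treat and says that analyses "will include service users that are included in the study, irrespective of how much intervention is received".

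**The concern.** Randomising LAs balances the populations of the LAs in expectation. It does not balance the people analysed if the intervention can influence who is counted. Two routes are open.

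- **Exit before the threshold.** A person supported by the nurse after, say, three sightings who then leaves the street never reaches six and is never in the trial. A similar person in a control LA may stay out, reach six and be counted.
- **Entry to the record.** Table 6 expects the nurse's presence to raise contact with service users. More or different contact can change who is assessed and given a baseline.

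The threshold matters for the outcome by the protocol's own reasoning: Section 6.1 justifies it partly because people who spend more time on the street are further from being housed.

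The estimate is meant to be used. Section 10.3 says that a further trial would be unnecessary if the interval showed benefit, and Section 10.4 carries the effect estimates into the sample size of a definitive trial. An estimate that mixes case mix with treatment effect would mislead in both uses.

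**Working it through.** **1. Does anything planned repair selection into the analysis set?**

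- The set in Section 10.1 starts from those included, so it inherits any difference in inclusion.
- Section 10.4 makes no baseline housing adjustment because everyone is rough sleeping at entry. Such an adjustment could not help.
- The age and gender covariates (Section 10.4) and the balance check (Section 10.7) use baseline characteristics of people already entered. None of those listed in Section 10.2 or Appendix F measures sightings or time on the street.
- The CONSORT flow (Section 10.2) counts service users included. It does not mention those who met the threshold but were not entered.
- Table 9 labels baseline outcomes as pre-intervention, but no rule secures this. The baseline may follow first contact by up to four weeks, and support before eligibility is allowed.

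**2. Yardstick: the planned precision.** Inputs from Section 9.1 and Table 10: 8 clusters per arm, 40 per cluster, ICC 0.1, 80% power, two-sided 5%, MDES 0.53.

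- Design effect = 1 + (40 - 1) × 0.1 = 4.9.
- SE of the standardised difference = √(2 × 4.9 / 320) = 0.175.
- MDES = (t₀.₉₇₅ + t₀.₈₀) × SE = 0.527 with 14 df and 0.530 with 13 df. The stated 0.53 is reproduced.
- On the percentage scale, SE = 100 × √(p(1 - p)) × 0.175, which is 7.6, 8.3 and 8.7 points at p = 25%, 35% and 45%. The MDES of 0.53 SD is 22.9, 25.3 and 26.4 points.

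**3. Size of the bias under assumptions.** The documents give no rates, so every input here is assumed. Let half of the eligible people be easier to house (6-month rate a) and half harder (rate b), with no true effect.

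- If a fraction f of the easier group leaves before the sixth sighting in intervention sites only: bias = -(a - b) × f / (2(2 - f)).
- If instead nurse contact adds a fraction f to the easier group: bias = +(a - b) × f / (2(2 + f)).

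Example with a = 60%, b = 10%, f = 0.5: -50 × 0.5/3 = -8.3 points, or +50 × 0.5/5 = +5.0 points.

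| a / b | Control rate | Easier group reduced by 10–50% | Easier group enlarged by 10–50% | Planned SE |
|---|---|---|---|---|
| 50% / 20% | 35% | -0.8 to -5.0 | +0.7 to +3.0 | 8.3 |
| 60% / 10% | 35% | -1.3 to -8.3 | +1.2 to +5.0 | 8.3 |
| 80% / 10% | 45% | -1.8 to -11.7 | +1.7 to +7.0 | 8.7 |

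With f at 10, 20, 30, 40 and 50% there are 30 combinations. Two exceed one SE: 80%/10% with 40% lost (-8.8) and with 50% lost (-11.7). Neither formula contains the sample size, so a larger trial would narrow the interval around the same bias.

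**The case against.** The best case against is that the protocol leaves much less room for this than it first appears.

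- Outreach workers are named with nurses for both eligibility and baseline in Table 9, and they support collection in intervention sites (Section 8.1). Table 7 accepts LA records alone.
- Nurses accompany the outreach team and should not go alone, and the team locates people (Table 6). Sightings made by a nurse without the team should be rare.
- The criterion looks back up to six months, so early entrants can qualify on sightings from 2024.
- Logbooks record nurse time on eligible and ineligible people (Section 6.1), and the process evaluation asks about reach and recruitment (Section 11.1.2).
- This is a pilot whose main outcome is feasibility (Section 7.1), and no p-values are reported.

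All of this stands as a limit on size and urgency. None of it fixes who is entered, and Sections 10.3 and 10.4 still use the estimate for decisions.

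Three stronger readings are tempting and are not supported. A reader might infer that anyone who declines the nurse, or sleeps outside nurse shifts, is lost; nothing stops the outreach team from entering that person. A reader might infer that control sites enter every eligible person; Section 7.2.4 states that intention for both arms but does not assure it. A reader might infer that the intervention arm does lose its quickest exits; support before the threshold is permitted, but nothing shows that it occurs or how often.

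**Conclusion.** The concern holds in a limited form. Allocation precedes identification, unmasked staff identify people during live delivery, and the nurse shares that task and may support people below the threshold in intervention sites only. Entry could therefore depend on the arm, and the 6-month housing estimate could be biased in either direction.

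The size cannot be obtained from the documents. On assumed rates with no true effect it ran from -11.7 to +7.0 points, mostly below one planned SE and well below the planned MDES of about 23 to 26 points. Exposure is partial. It is least for people entered early in 2025 and grows over the ten-month baseline period as more of the sightings fall within delivery.

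This should be fixed before analysis. It does not invalidate the pilot or its feasibility results.

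**What to change.** (a) Pre-specify a sensitivity analysis of the primary outcome restricted to people whose six sightings were complete before nurse delivery began in that LA and, in control LAs, before the matching calendar date. Use dated sightings from LA outreach records. This assumes that they can be extracted, which is plausible because the criterion requires sightings to be counted.

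(b) Report by arm and LA the numbers who met the threshold, were entered with a baseline, and were not entered, plus nurse contact before baseline. This covers the entry route, which (a) alone does not close.

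(c) State that the primary estimate, and the remark in Section 10.3 about not needing another trial, will be read in light of (a) and (b).

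(d) For a definitive trial, define the eligible list in both arms from outreach-team records, fixed before delivery starts.

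**Cost.** Protocol wording, one data extract and one analysis. The restricted set is smaller. If half of each cluster remained (an assumption) and the ICC stayed at 0.1, the design effect would be 1 + 19 × 0.1 = 2.9 and the SE √(2 × 2.9/160) = 0.190 against 0.175, about 9% wider. Entry percentages may look lower once people not entered are counted. Version 3.1 is dated 21.10.2025, as baseline collection closes, so missed baselines cannot be recovered.

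**What would not help.** Dating eligibility at the team's sixth sighting still drops people housed before it. Discounting sightings made by a nurse alone changes little, since nurses go out with the team. Adding people never approached to the denominator supplies no outcomes, and Section 10.8 plans no imputation.

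Nurse support to other people need not change.
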